5.1.3 Treatment Compliance

WAS:

If the subject is discharged while continuing treatment with intravenous dosing, the subject must return to the research facility or other approved facility every day to receive the daily dose. Vital signs will be taken pre and post dose. Infusion reaction and other safety monitoring will be conducted.

Subjects who are discharged from the hospital with oral capsules for at-home administration must return weekly for study drug accountability and to receive new oral dosing supplies. Subjects will be provided with 1 week worth of study medication, instructions and a daily dosing log for documentation of ingestion of the oral study medication.

Study subjects and their parents/legal guardians should be counseled on the need to meet 100% compliance with study drug. Investigator or designee should ensure that study subjects meet this goal throughout the study period.

The date and time of dosing will be recorded once the first capsule is ingested. The subject should ingest the entire dose within 5 minutes. If the entire dose is not ingested within 5 minutes, record the reason for dosing delay in the source documentation. If the subject should vomit any of the medication, this is to be recorded as well. The dose is NOT to be repeated. Compliance of the study drug will be monitored by the accounting of unused medication returned by the subject at visits. Compliance will be verified by the accounting of study drug at the weekly visits after day 7 and/or at the EOT visit.

When study drug is administered at the research facility, it will be administered under the supervision of study personnel. A subject daily dosing log will be collected to record date/time and completeness of dosing for each day.

IS AMENDED TO:

If the subject is discharged while continuing treatment with intravenous dosing, the subject must return to the research facility or other approved **location** every day to receive the daily **intravenous** dose. Vital signs will be taken pre and post dose. Infusion reaction and other safety monitoring will be conducted.

Subjects who are discharged from the hospital with oral capsules for at-home administration must return weekly for study drug accountability and to receive new oral dosing supplies. Subjects will be provided with **approximately** 1-week worth of study medication, **dosing** instructions and a daily dosing log for documentation of ingestion of the oral study medication.

~~Study subjects and their parents/legal guardians should be counseled on the need to meet 100% compliance with study drug. Investigator or designee should ensure that study subjects meet this goal throughout the study period.~~

The **subject or parent/legal guardian must record the date and time of oral** dosing ~~will be recorded~~ once the first capsule is ingested. The subject should ingest the entire dose within 5 minutes. If the entire dose is not ingested within 5 minutes, record the reason for dosing delay in the source documentation. If the subject should vomit any of the medication, this is to be recorded as well. The dose is NOT to be repeated. Compliance of the study drug will be monitored by **review of the oral dosing log and** the accounting of unused medication returned by the subject at each scheduled visits. ~~Compliance will be verified by the accounting of study drug at the weekly visits after day 7 and/or at the EOT visit.~~

When study drug is administered at the research facility, it will be administered under the supervision of study personnel. A subject daily dosing log will be collected to record date/time and completeness of dosing for each day.

Study subjects and their parents/legal guardians should be counseled on the need to meet 100% compliance with study drug dosing. The investigator or designee should ensure that study subjects adhere to this goal throughout the study.

5 Treatments and Evaluation

5.3.2 Pharmacokinetic Assessment

WAS:

In addition to the above, 24-hour pharmacokinetic samples for intravenous or oral dosing will be obtained on any day between day 14 and day 42, while the subject is still receiving study drug, for subjects who consent to participation in the 24-hour pharmacokinetic assessment.

IS AMENDED TO:

In addition to the above, 24-hour pharmacokinetic samples for intravenous or oral dosing will be obtained on any **one** day between day 14 and day 42, while the subject is still receiving study drug, for subjects who consent to participation in the 24-hour

pharmacokinetic assessment.

5 Treatments and Evaluation

5.3.3 Oral Dosing Acceptability Assessment

ADDED:

Refer to [Appendix 12.7 Oral Dosing Acceptability Assessment].

5 Treatments and Evaluation

Table 4 Total Amount of Blood Drawn

WAS:

Table 4 Total Amount of Blood Drawn

IS AMENDED TO:

Table 7-4 Total Amount of Blood Drawn

IV: intravenous;

10 Study Organization

10.1 Data and Safety Monitoring Board (DSMB)

WAS:

The DSMB members will not be employees of Astellas nor otherwise involved with the study conduct.

IS AMENDED TO:

The DSMB members will not be employees of Astellas nor otherwise involved with the study conduct; **however, members of the DSMB could be members of the AC.**

10 Study Organization

10.2 Adjudication Committee (AC)

WAS:

The AC members will not be employees of Astellas nor otherwise involved with the study conduct.

IS AMENDED TO:

The AC members will not be employees of Astellas nor otherwise involved with the study conduct; **however, members of the AC could be members of the DSMB.**

12 Appendices

ADDED:

12.7 Oral Dosing Acceptability Assessment

SITE NUMBER: _____

DATE: ____ / ____ / ____ (DD/MMM/YYYY)

SUBJECT NUMBER: _____

General Instructions

The questionnaire will be completed for all subjects who received oral study medication:

- By the patient him/herself (when the patient is able to do so), or
- By the parent/legal guardian/study nurse (based on input from the patient).

The questionnaire will be completed:

- Following the first oral dose (shortly after taking the study medication).

[figure not shown]
Subject Instructions

You have just taken the oral study medication.

[figure not shown]
- Please answer the three questions below.
- Put a cross in the box below the best answer.
- If you make a mistake, cross it out with a single line and cross the correct answer. The original entry should still be legible.

Questions

1. How was the TASTE of the medication?

2. How was it to SWALLOW the medication?

[figure not shown]

SITE NUMBER: _____

DATE: _____ (DD/MMM/YYYY)

SUBJECT NUMBER: _____

3. How would you FEEL if you took the medication again?

| ICH | International Conference on Harmonization |
| IFD | Invasive Fungal Disease |
| IM | Invasive Mucormycosis |
| INR | International normalized ratio |
| IV | Intravenous |
| K-M | Kaplan-Meier |
| LLOQ | Lower Limit of Quantification |
| MedDRA | Medical Dictionary for Regulatory Activities |
| N | Sample Size |
| PD | Protocol Deviation |
| PK | Pharmacokinetic |
| PKAS | Pharmacokinetics Analysis Set |
| PPK | Population Pharmacokinetics |
| PT | Preferred Term |
| PTT | Partial thromboplastin time |
| QTc | Corrected Q-T Interval |
| SAE | Serious Adverse Event |
| SAF | Safety Analysis Set |
| SAP | Statistical Analysis Plan |
| SAS | Statistical Analysis Software |
| SD | Standard Deviation |

| Abbreviations | Description of abbreviations |
|----------------------|-------------------------------------|
| AC | Adjudication Committee |
| SOC | System Organ Class |
| TBL | Total bilirubin |
| TEAE | Treatment Emergent Adverse Event |
| TLF | Tables, Listings and Figures |
| ULN | Upper Limit of Normal |
| US | United States |
| WHO | World Health Organization |

List of Key Terms

| Terms | Definition of terms |
|------------------------|--|
| Adverse Event | An adverse event (AE) is any untoward medical occurrence in a subject or clinical investigation subject who has been administered a pharmaceutical product (remark: this means any investigational medicinal product) and which does not necessarily have a causal relationship with this treatment. An AE can therefore be any unfavorable and unintended sign (including an abnormal laboratory finding), symptom, or disease temporally associated with the use of a medicinal product, whether or not related to the medicinal product. |
| Baseline | Baseline is the time point prior to the first dose of study medication. The last measurements/evaluation prior to first dose of therapy is considered the baseline measure/evaluation. |
| Investigational period | Period of time where major interests of protocol objectives are observed, and where the test drug is usually given to a subject, and continues until the last assessment after completing administration of the test drug as stated in the protocol regarding V5 (End of Trial). |
| Screening | Process for retrieving candidates for the study. Process for checking the eligibility of subjects usually done during the “pre-investigational period”. Screening evaluations will be performed on the same day of study enrollment. |
| Screening failure | Evaluated subject but did not fulfill protocol inclusion and/or exclusion criteria and failed to receive randomized or open label study treatment or decided not to participate anymore (withdrew consent) prior to completing pre-investigational treatment period. |

| | |
|-----------------------|---|
| Serious Adverse Event | An adverse event is considered “serious” if, in the view of either the investigator or sponsor, it results in any of the following outcomes: results in death; a life-threatening adverse drug experience (subject is at immediate risk of death.); insubject hospitalization or prolongation of existing hospitalization, not associated with planned study procedures; a persistent or significant disability/incapacity; or a congenital anomaly/birth defect in the offspring of a subject who received study drug or a medically important events that may not be immediately life threatening or result in death or hospitalization but may jeopardize the subject or may require intervention to prevent one of the other outcomes listed above. |
|-----------------------|---|

1 INTRODUCTION

This Statistical Analysis Plan (SAP) contains technical and detailed elaboration of the principal features of the analysis described in the protocol, and includes procedures for executing the statistical analysis to fulfill the objectives of the study.

Changes to the planned analyses in the final SAP will be justified in the Clinical Study Report (CSR).

2 STUDY OBJECTIVE(S) AND DESIGN

2.1 Study Objective(s)

Safety Objective: To evaluate the safety and tolerability of isavuconazonium sulfate in pediatric subjects.

Efficacy Objective: To assess the efficacy of isavuconazonium sulfate for the treatment of invasive Aspergillosis (IA) or invasive Mucormycosis (IM) in pediatric subjects.

Pharmacokinetic Objective: To evaluate the pharmacokinetics of isavuconazole by monitoring the plasma concentrations in pediatric subjects during treatment with isavuconazonium sulfate.

2.2 Study Design

This is a phase 2, open-label, non-comparative, multicenter study to assess the safety, efficacy and pharmacokinetics of isavuconazonium sulfate in pediatric subjects for the treatment of IA or IM.

An approved informed consent form (ICF) must be obtained from the subject’s parent or legal guardian, and, if required, child assent prior to any study related procedures being performed.

Approximately 30 centers in the United States (US) and European Union (EU) are planned to enroll approximately 30 subjects ages 1 to < 18 years of age

The subjects will enter into screening anytime between days -5 to day 1 (predose). All subjects will be assigned to open-label treatment. Treatment will begin on day 1 and then subjects are followed for 60 days after the last dose for safety. Treatment will be administered until the subject has a successful outcome as judged by the investigator or for a maximum duration of 84 days (IA) or 180 days (IM), whichever occurs first.

After successful screening, all subjects will receive a loading regimen of isavuconazonium sulfate, which consists of a dose every 8 hours (\pm 2 hours) on days 1 and 2 (for a total of 6 doses), followed by once daily maintenance dosing for up to 84 days (IA) or day 180 (IM) of dosing. The first maintenance dose should start 12 to 24 hours after the administration of the last loading dose. Subsequent maintenance doses will be administered once daily (24 hours \pm 2 hours from the previous maintenance dose).

Blood sampling for the analysis of trough levels will be obtained from all subjects. The samples should ideally be drawn immediately prior to the next dose of study medication, but must be taken no earlier than 1 hour prior to the next dose on days 7, 14, 21, 42 and 84 or end of treatment (EOT). **In addition to the above, 24-hour pharmacokinetic samples will be obtained on any day between day 14 and day 42, while the subject is still receiving study drug, for subjects that consent to participation in the 24-hour pharmacokinetic assessment.** No additional samples are taken from IM subjects between day 84 through day 180.

Throughout the study, safety and tolerability will be assessed by the recording of AEs, vital signs, electrocardiograms (ECGs) and safety laboratory evaluations. All subjects will complete 2 follow-up visits (via telephone at the discretion of the investigator), 30 and 60 days, after the subject's day 84 (IA) /day 180 (IM) or EOT visit.

If subject discontinues study drug prior to day 84 or day 180 (for IM), all EOT procedures must be completed. If subject continues to allow consent, end of study (EOS) information will be collected 30 and 60 days after EOT.

Details of the schedule of clinical assessments are available in the protocol.

2.3 Randomization

This is an open-label study with no randomization.

3 SAMPLE SIZE

The sample size of approximately 30 subjects is planned. No formal sample size calculation was performed.

Evaluable subjects are subjects that have received at least 1 dose of study drug. Every effort will be made to achieve at least 5 evaluable subjects per age cohort: 1 to < 12 years of age and 12 to < 18 years of age. The sponsor reserves the right to stop enrollment if the cohort

requirements are not achieved. There will be no replacements for any subject that is enrolled but later determined to be non-eligible.

4 ANALYSIS SETS

In accordance with International Conference on Harmonization (ICH) recommendations in guidelines E3 and E9, the following analysis sets will be used for the analyses.

The determination of whether subjects are included or excluded from the safety and efficacy analysis sets may require using data which will arrive after database hard-lock.

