5.3 Efficacy and Pharmacokinetic Assessments

5.3.1 Efficacy Assessment

All clinical, mycological, radiological assessments and diagnostic tests performed to document the baseline mould infection must be recorded. Criteria for possible, probable and proven disease based on the EORTC/MSG criteria require evidence including host factors (neutropenia, hematological malignancy, etc.), mycological criteria (positive culture from normally sterile site, BAL fluid, serum or BAL GM and histology of tissue demonstrating the

presence of fungal elements), and clinical signs and symptoms (radiological evidence of fungal disease at the infected body site). These data will be recorded in the eCRF.

During treatment with study drug, record any tests performed to demonstrate changes from baseline or evaluate the status of the fungal infection, such as mycological evidence of fungal culture or histology results (positive and negative) from the relevant site of infection or any new site, new fungal infection, changes in clinical signs and symptoms, including radiological findings relevant to the baseline fungal infection under treatment, and any serological markers performed (serum GM) and any surgical procedures. Record any procedures conducted to further assess or treat the fungal infection such as surgical debridement, amputation, etc. and the results of such procedures. Negative results of tests demonstrating resolution of infection should also be documented and recorded in the eCRF. Mortality status will be assessed per [Table 1 and Table 2 Schedule of Assessments].

Every effort should be made to speciate and characterize any fungal organisms grown in cultures. Results of susceptibility testing done locally will be collected. Fungal isolates from all positive fungal cultures should be stored and a reference laboratory will be made available by the sponsor. The reference laboratory will provide confirmation of the fungal genus and species, as well as in vitro susceptibility to isavuconazole, as well as relevant mould-active antifungal drugs. The reference laboratory results will not be available until after the end of the study.

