7.2 Analysis Sets

Detailed criteria for analysis sets will be laid out in classification specifications and the allocation of subjects to analysis sets will be determined prior to database hard-lock.

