4.1 Full Analysis Set

The full analysis set (FAS) will consist of all subjects who are enrolled and receive at least one dose of study drug. This will be the primary analysis set for efficacy analyses.

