4.2 Modified Full Analysis Set

The modified FAS (mFAS) will consist of the subset of the FAS subjects who have either probable or proven IA or IM diagnosis at baseline or up to 10 days after first dose. Subjects with a possible diagnosis of IA or IM will not be included in this subset. The mFAS will be a secondary analysis set for efficacy analyses. Select demographic and baseline characteristics may also be summarized for the mFAS.

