6.2.5 Baseline IFI

The descriptive summary includes subjects in each category of fungal infection site and fungal culture organism(s) by genus at baseline using the FAS and mFAS populations. Baseline will include all data collected from Day -28 to Day 10, as relevant. These include Host factors, Clinical factors, Mycological Criterion and Other invasive fungal disease (IFD) signs.

In addition, categorization of patient's fungal infection will include Proven, Probable or Possible. This categorization is evaluated again on Day 10. Day 10 may provide more information than baseline given time for additional confirmatory laboratory results for subjects that may upgrade or downgrade fungal diagnosis. For example, a final baseline evaluation of subject status Proven, Probable or Possible will be determined using the combination of data collected.

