6.4.1.3 Sensitivity Analysis for Primary Efficacy Endpoint

The primary efficacy endpoint will be analyzed as in Section 6.4.1.1 using the mFAS population. In addition mFAS patients taking excluded concomitant medications used to treat IFDs will be eliminated for analysis of primary endpoint.

A secondary sensitivity analysis will apply a condition on the crude success rate of overall outcome of treatment evaluated by the AC on Day 42. Patients who die before or on Day 42 will be considered failures even if the DRC considers them successes. The crude success rate of overall outcome of treatment evaluated by the AC at Day 42 incorporating this condition will be summarized. A 95% CI for this crude success rate of overall outcome of treatment evaluated by the AC at Day 42 will be calculated using exact confidence limits. This sensitivity analysis will only be performed if any patient died by Day 42 is considered a success for treatment by the AC.

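### The SAP lets analysis-set membership rest on data arriving after hard-lock, against the protocol, which leaves the mFAS open to change after lock

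*SAP*

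**What the plan says.** On when analysis sets are settled, the two documents give opposite rules:

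- Protocol 7.2: "the allocation of subjects to analysis sets will be determined prior to database hard-lock". The detailed criteria are left to separate classification specifications.
- SAP 4, of the safety and efficacy sets: the determination "may require using data which will arrive after database hard-lock".

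The sets concerned differ in what they need:

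- SAP 4.1: the FAS "will consist of all subjects who are enrolled and receive at least one dose of study drug". SAP 4.3 states that the SAF is the same set.
- SAP 4.2: mFAS subjects must "have either probable or proven IA or IM diagnosis at baseline or up to 10 days after first dose". On its role: "The mFAS will be a secondary analysis set for efficacy analyses".

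Three other places bear on the point:

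- SAP 6.2.5 has the diagnostic category reassessed on Day 10, because there may then be "additional confirmatory laboratory results for subjects that may upgrade or downgrade fungal diagnosis".
- Protocol 5.3.1, on confirmation of genus and species and on susceptibility testing: "The reference laboratory results will not be available until after the end of the study".
- SAP 6.4.1.3: "The primary efficacy endpoint will be analyzed as in Section 6.4.1.1 using the mFAS population". SAP 6.4.2 and 6.4.3 also report Day 84 and EOT mortality and the response endpoints in the mFAS.

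**The concern.** Settling analysis sets before lock prevents membership from being revised once the final outcome data and tables exist, and it leaves a decision that can be audited. The SAP sentence removes that protection. It does not say which data may arrive late, until when they count, who applies them, or whether that person may know the subject's outcome. The SAP's revision tables (sections 7.1 and 7.2) hold only blanks and placeholders, so no reason for departing from the protocol is recorded.

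At stake are the analyses restricted to confirmed infection. If subjects enter or leave the mFAS after their vital status and response are locked, its mortality and response rates could be selected, even unintentionally. With about 30 subjects planned in total, each reclassified subject carries visible weight.

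**Working it through.** **Step 1. Is the conflict real?** Protocol 7.2 and SAP 4 are both current text and address the same act, allocation of subjects to analysis sets. One requires it before hard-lock without exception; the other allows it to depend on data arriving afterwards. A set that needs post-lock data cannot be settled before lock. The conflict stands on the wording alone.

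**Step 2. Which sets can the SAP sentence affect?**

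- FAS and SAF: enrolment and one dose. Late data could hardly change either.
- mFAS: a diagnostic category reached by Day 10. SAP 6.2.5 expects that category to move as results come in. Neither SAP 4.2 nor SAP 6.2.5 says whether a result reported later from an early specimen counts.
- PKAS: not covered, since the SAP sentence names only the safety and efficacy sets.

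The mFAS is therefore the set realistically exposed.

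**Step 3. Is a late data source identified?** SAP 4 names none. Reference-laboratory results are one candidate. Protocol 5.3.1 places them after the end of the study, which Protocol 9 defines by the last participant's last visit or procedure. Neither document equates that date with hard-lock, and neither says these results decide mFAS membership. The source remains a possibility only.

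**Step 4. How far could the rate move?** The plan gives no figure to reproduce. The following is an illustration.

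Inputs:

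- mFAS size *n*: not given; assumed to be 10 to 25, within the roughly 30 subjects planned (Protocol 7.1).
- Mortality: 30%, borrowed from the 12-week figure for a prospective multinational paediatric cohort in Protocol 1.1. It is an assumption here, not a forecast of Day 42 mortality.
- Deaths *x*: 0.30 × *n*, rounded to a whole number with halves upward, giving 3, 5, 6 and 8 for *n* = 10, 15, 20 and 25.

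The exact (Clopper-Pearson) 95% limits are the 2.5% quantile of Beta(*x*, *n* − *x* + 1) and the 97.5% quantile of Beta(*x* + 1, *n* − *x*). Removing one death changes the rate by *x*/*n* − (*x* − 1)/(*n* − 1) = (*n* − *x*)/[*n*(*n* − 1)].

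| Start | After removing one death | Fall in rate |
|---|---|---|
| 3/10 = 30.0% (6.7 to 65.2) | 2/9 = 22.2% (2.8 to 60.0) | 7/90 = 7.8 points |
| 5/15 = 33.3% (11.8 to 61.6) | 4/14 = 28.6% (8.4 to 58.1) | 10/210 = 4.8 points |
| 6/20 = 30.0% (11.9 to 54.3) | 5/19 = 26.3% (9.1 to 51.2) | 14/380 = 3.7 points |
| 8/25 = 32.0% (14.9 to 53.5) | 7/24 = 29.2% (12.6 to 51.1) | 17/600 = 2.8 points |

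Reclassification can also raise the rate. Adding one death gives 4/11 = 36.4% from 3/10 and 9/26 = 34.6% from 8/25, rises of 6.4 and 2.6 points. Adding one survivor has a smaller effect: 3/11 = 27.3% and 8/26 = 30.8%, falls of 2.7 and 1.2 points.

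**Step 5. Does the primary result move?** No. SAP 6.4.1.1 divides deaths by the number of FAS subjects, and FAS membership does not depend on diagnosis.

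**The case against.** The strongest case on the other side is that this is a drafting slip with little consequence. The SAP sentence also covers the safety set, which late data could hardly affect, and the SAP still carries unfilled template text. The primary analysis and a full set of secondary results use the FAS. The study is descriptive, with no formal inference. The shifts above are small beside exact intervals some 38 to 59 points wide, and they show only that one subject matters in a small sample. Unseen documents (the classification specifications and the Adjudication Committee charter) may set tighter rules.

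Much of this stands, and it limits the point. It does not remove the conflict: a slip in a governing document still has to be corrected, and other documents would not reconcile these two sentences.

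A reader might also infer more than the documents support:

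- *That reference-laboratory results will reassign subjects after lock.* Their arrival is tied to study end, not hard-lock, and no text gives them that role.
- *That the mFAS rates will be biased.* The sentence permits a route to bias; it does not show that the route will be used, or in which direction.
- *That a pre-lock rule would make classification blind to outcome.* The trial is open-label, so survival is visible before lock, and Protocol 10.2 has the same committee confirm both diagnosis and response. The rule stops later changes; it does not blind earlier ones.
- *That the protocol already fixes the IA/IM/mixed grouping before lock.* Protocol 7.2 concerns analysis sets only.

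**Conclusion.** The contradiction is certain and should be corrected. As written, the SAP leaves membership of the mFAS open after the final outcome data are locked, without a named data source, cut-off or decision-maker. This could bias the secondary mFAS mortality and response rates. It carries no type I error consequence in a descriptive study.

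The size is illustrative: about 3 to 8 percentage points of mFAS mortality for each death removed, if the mFAS has 10 to 25 subjects and mortality is near 30%. Confidence is high in the textual conflict and in the mFAS being the exposed set. It is lower for any particular late data source, because none is named.

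**What to change.** Delete the sentence in SAP 4 and state, as Protocol 7.2 does, that allocation to analysis sets is determined before database hard-lock.

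Three additions go beyond the protocol's rule and should be presented as such:

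1. Fix mFAS membership and the IA/IM/mixed grouping at the same time, from the adjudicated diagnosis using data through Day 10.
2. Preferably have that diagnosis made without sight of vital status or response, because the pre-lock rule alone does not achieve this.
3. For laboratory results that come late, either hold the lock until they arrive or use them only in a labelled sensitivity analysis or listing.

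The core correction is one SAP sentence. The additions need a few more lines in the SAP and possibly in the committee's charter. The main cost is that the adjudicated diagnosis must be complete before lock; holding the lock for late results would also cost time. Nothing changes for subjects, sites or sample size.
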